## 4.1 Enrollment period

### 4.1.1 Screening visit – Visit 1 (Week -2)

Each patient will provide written informed consent prior to any study-specific procedures and will undergo assessments applicable for each visit as outlined in [Table 1](#). Registration of the patient's enrollment via IWRS/IVRS should occur on the day that Visit 1 procedures are performed.

At screening, consenting patients will be assessed to ensure that they meet all eligibility criteria. Visit 1 assessments are primarily concerned with assessment of eligibility (inclusion/exclusion criteria), including asthma disease state, requisite level of severity based on background medications and eosinophil count.

Demographic information, including date of birth, age, sex, race, and ethnicity, will be collected during the screening visit as per local regulations. All patients who are not already taking prednisone/prednisolone as their OCS treatment will be switched to prednisone/prednisolone. Testing of prednisone/prednisolone levels will be done only for patients who switch to prednisone/prednisolone. If this test is required, all laboratory tests should be delayed by 3 to 7 days after having switched the OCS ([Appendix F](#)). Prednisone/prednisolone levels should be measured approximately 1 to 2 hours after prednisone/prednisolone intake on the same day.

At the screening visit, blood samples will be collected for assessments such as laboratory tests, genomic analysis, serum biomarkers, total IgE, Phadiatop test, EDN, eosinophil count, etc., as mentioned in [Table 1](#). Current, regular use of a high-dose ICS and LABA for  $\geq 6$  months prior to enrollment will be recorded. Additionally, patients must be on chronic daily OCS therapy (equivalent to  $\geq 5$  mg/day of prednisone) for  $\geq 3$  continuous months directly preceding Visit 1, and this must be documented in the medical records. Inhaled corticosteroids and LABAs may have been administered as either a fixed dose or 2 separate inhalers and must be consistent with the highest approved maintenance dose in the local country (Inclusion Criterion 6). A stable dose of OCS must have been maintained for  $\geq 4$  weeks prior to Visit 1.

Patients can proceed directly to Visit 2 once central laboratory results are received, and all eligibility requirements are confirmed. Visit 2 should be done up to 2 weeks after Visit 1. For patients switching to prednisone/prednisolone at V1 and who thus require a delay in laboratory tests, Visit 2 can be done up to 2 weeks after the collection of laboratory samples. Patients will continue to receive treatment with their current ICS/LABA and other controller(s) (if applicable) with no changes.

If the patient experiences an asthma exacerbation during screening that requires evaluation in an urgent care center or emergency department, hospitalization, or temporary increase (bolus/burst) of systemic steroids, they will not be screen failed, but an extension of the screening period up to 3 months will be allowed to ensure that the patient recovers from the asthma exacerbation and the OCS dose is stabilized. Additionally, if a patient experiences acute upper/lower respiratory infection that requires antibiotics or antiviral medication during

screening, then they also will not be screen failed and an extension of the screening period of up to 3 months will be allowed. If the patient recovers from the asthma exacerbation or acute upper/lower respiratory infection and is stable for  $\geq 2$  weeks, then the patient will be allowed to continue in the study. Patients must enter the treatment phase within 3 months of screening; if it has been longer than 3 months, then the patient may be rescreened.

If the patient experiences a non-asthma related event requiring temporary increase (bolus/burst) of systemic steroids, an extension of the screening period of up to 3 months may be allowed (AZ study physician can be consulted if required).

Patient's eligibility should be evaluated at the screening visit with the relevant documentation entered in the source and eCRF.

#### **4.1.2 Rescreening**

Rescreening of patients for any reason will be allowed only once for each patient and only upon approval of the AstraZeneca Physician. Patients will keep the same e-code.

### **4.2 Open-label treatment period**

The open-label treatment period is divided into 3 phases based on the OCS dose adjustment: induction phase (Section 4.2.1), reduction phase (Section 4.2.2), and maintenance phase (Section 4.2.3). Patients will complete the ACQ-6 and maintenance medication assessment weekly using the ePRO throughout the treatment period (see Section 5.3.4 for details).

#### **4.2.1 Induction phase**

The induction phase will start at Visit 2 (Week 0) and will continue until the day prior to Visit 3. Inclusion and exclusion criteria will be confirmed at Visit 2 and the patient will complete the ACQ-6, maintenance medication assessment, and SGRQ on the ePRO, prior to benralizumab administration, to establish baseline scores. Additionally, during the induction phase only, patients will complete the Patient Global Assessment of Change (PGIC) on a weekly basis on the ePRO in addition to weekly completion of the ACQ-6 and maintenance medication assessments. All patients who meet eligibility criteria and enter the study will receive open-label benralizumab. The first dose of the study drug will be administered SC as Q4W dosing at Visit 2. Patients will be observed at the site for 2 hours after dosing. During this time, patients will remain on their regular asthma controller medications, and no dose adjustments to OCS will be made. Patients who experience asthma exacerbations that require evaluation in an urgent care center or emergency department, hospitalization, or temporary increase of systemic steroids (bolus/burst dosing) will be managed as per Section 5.2.3.

#### **4.2.2 OCS Reduction phase**

The reduction phase will start at Visit 3 (Week 4) after the dose of benralizumab, and subsequent OCS dose reductions will occur according to the schema defined for each baseline OCS dose until patients reach a 5 mg/day dose (Table 2).

The study drug will be administered SC as Q4W dosing up until the third dose of benralizumab (therefore at Visits 3 and 4 during the OCS reduction phase) and then Q8W thereafter (8 weeks between the 3rd and 4th benralizumab dose). Patients will be observed at the site for 2 hours after dosing for the first 3 study drug administrations (therefore at Visits 3 and 4 during the OCS reduction phase) and for 1 hour after subsequent study drug administrations for any acute drug reactions.

For all patients, HPA axis integrity will be evaluated after 4-weeks on 5 mg/day and prior to tapering down the OCS dose (for patients with baseline OCS doses equal to 5 mg/day, this will be assessed 4 weeks after the first dose of benralizumab administration and before initiation of the OCS reduction phase)

First, a screening method with morning serum cortisol is done (8-9 am morning cortisol level), to evaluate whether the patient has:

- Normal cortisol levels
- Complete AI

Cortisol levels from the morning cortisol test that are below normal range and above the Complete AI range are considered “Indeterminate;” and require additional testing described below.

Secondly, the ACTH stimulation test (ie, Synacthen®, Cortrosyn™) is done within approximately 1 week in the subset of patients with indeterminate results from the morning cortisol test [see also Section 5.2.1.2 for details]. The ACTH stimulation test is more specific than the morning cortisol test, and can determine whether the patient has:

- Normal cortisol levels
- Complete AI
- Partial AI

Dose reduction of OCS should be interrupted if the patient suffers an asthma exacerbation (Section 5.2.3) or in case the Investigator considers the patient to be having a significant deterioration of his/her asthma disease (Section 5.1.2.1). After the OCS bolus/burst to treat an exacerbation is completed, or after recovery from an asthma deterioration, the Investigator may either return the OCS dose to a one-step higher dose level (or more if considered necessary by the Investigator) than what was prescribed when the exacerbation or asthma worsening occurred or continue with the same OCS dose, which must be maintained at a stable dosage for at least two weeks.

After recovery from the first exacerbation or asthma deterioration, the patient will be allowed to proceed with another attempt to reduce their OCS dose; however, the patient will follow a lower speed for OCS down-titration (reductions Q4W; [Table 3](#)).

In case of a second exacerbation or asthma deterioration, no further OCS dose reduction will be allowed, and the patient will remain on the same OCS dose or return to a one-step higher dose level (or more as considered necessary by the Investigator) than what was prescribed

when the exacerbation/worsening occurred. The OCS dose reduction phase will then be terminated, and the patient will enter the maintenance phase. Further details are provided in Section [5.2.3](#).

Patients who experience asthma exacerbations that require evaluation in an urgent care center or emergency department, hospitalization, or temporary increase of systemic steroids (bolus/burst dosing) will be managed as per details in Section [5.2.3](#).

To help investigators evaluate the occurrence of a significant asthma deterioration, investigators will have access to the patient's weekly ACQ-6 scores (completed by means of an ePRO). A significant deterioration is defined as a worsening in ACQ-6 score of at least 0.5 from value at Visit 2. If the ACQ-6 score at Visit 2 is missing, the 1st score recorded post-Visit 2 and pre-OCS reduction may be used as baseline for the 0.5-point increase (note, however, that it will not be used to impute the baseline value for ACQ-6 analysis). Investigators should consider this information together with any other information reported by patients on signs/symptoms of the disease as well as compliance with maintenance asthma therapy. Based on the totality of the information, investigators can decide whether the patient can continue with the OCS dose reduction until the patient reaches an OCS dose of 0 mg/day (or lowest OCS dose possible in case no further OCS down-titration is allowed because of the presence of AI as measured by cortisol levels or in case of inadequate asthma control) without losing asthma control. The other patient-reported outcomes (PROs) will be carried out per the schedule in [Table 1](#).

The length of the benralizumab treatment period will depend on the baseline OCS dose, occurrence of asthma exacerbation(s) or asthma worsening, and whether the patient experiences AI. Procedures specific for the visits are listed in [Table 1](#). Restrictions as set out in Section [3.5](#) will continue to apply throughout the treatment period.

From Visit 3 onwards, the dose of OCS may be reduced only when conditions listed in Section [5.1.2](#) are met. The reductions will occur at an interval according to the titration schedule. The first OCS dose reduction can occur at Visit 3 after the dose of benralizumab at the site.

Patients will reduce OCS following confirmation from the Investigator/study site personnel at site visits or via telephone calls. Phone calls can be scheduled as required to assess the occurrence of exacerbations, asthma control (ACQ-6 scores), AEs, and concomitant medication use. Additional site visits can be scheduled for patients in case of poor asthma control.

[Table 2](#) depicts the proposed dose reduction schedule, provided the patient does not experience an exacerbation, worsening of asthma control, or AI. In case of asthma exacerbation or worsening, the dose reduction schedule will be longer ([Table 3](#)) and will vary depending on HPA axis integrity and/or on the patient's recovery from an exacerbation.

Depending on the baseline OCS dose and on the possibility of experiencing AI symptoms, each patient will spend a different amount of time in the reduction phase and the number of visits will be adjusted accordingly.

Approximately 1-2 weeks prior to end of the OCS reduction phase, the patients who have Partial AI, will undergo an additional morning cortisol test (and if required, ACTH stimulation test for indeterminate result) at the end of the OCS Reduction phase.

#### **4.2.3 Maintenance phase**

A patient will enter the approximately 24- to 32-week maintenance phase when they reach an OCS dose of 0 mg/day (or lowest OCS dose possible in case no further OCS down-titration is allowed because of the presence of AI as measured by cortisol levels or in case of inadequate asthma control) without losing asthma control. This could be earlier if OCS dose reduction fails due to clinical deterioration or if the patient experiences an asthma exacerbation. The duration of the maintenance phase will depend on when the patient enters the maintenance phase relative to the dosing cycle of benralizumab. During this phase, patients will continue benralizumab Q8W for 3 doses and then the EOT visit will be scheduled 8 weeks ( $\pm$  7 days) after the last dose of benralizumab (assessments performed as per [Table 1](#)). However, if during this period, the patient experiences asthma deterioration or an exacerbation, the length of the maintenance phase will not be extended and the patient will continue on 3 doses of benralizumab Q8W. Additionally increases in the maintenance OCS dose due to an asthma exacerbation is permitted per investigator discretion. Patients who experience an asthma exacerbation that requires evaluation in an urgent care center or emergency department, hospitalization, or temporary increase of systemic steroids (bolus/burst dosing) will be managed as per details in Section [5.2.3](#).

Patients who have Complete AI or Partial AI at the end of the OCS Reduction phase, will undergo a final morning cortisol test (and if required, ACTH stimulation test for indeterminate result) approximately 1-2 weeks prior to end of the OCS Maintenance phase (prior to EOT visit).

Patients will return the ePRO at the EOT visit. Completion of the treatment will be registered in IWRs/IVRs at the EOT visit for each patient. After stopping study drug, the patient will be adjusted to a post-study asthma maintenance regimen (which may include a respiratory biologic, if needed), per Investigator discretion.

Patients who prematurely discontinue study drug (see [Section 3.6](#)) should return to the study site and complete procedures described for the IPD visit and follow-up visit within 4 weeks ( $\pm$  7 days) and 12 weeks ( $\pm$  7 days) after the last dose of study drug, respectively. Study assessments and procedures to be performed at the IPD and follow-up visits are outlined in [Table 1](#). Reasons for premature discontinuation of study drug should be recorded in the eCRF.

#### **4.3 Follow-up period**

All patients who complete the maintenance phase or who prematurely discontinue study drug will have a follow-up contact after 12 weeks of the last dose of benralizumab. The follow-up contact can be done either on-site or via telephone contact. During this visit, patients will be assessed for any ongoing safety issues, and AEs and concomitant medications will be collected. Patients who have Partial AI or Complete AI at the end of the Maintenance phase, should be followed-up by an endocrinologist or other appropriate specialist, if deemed necessary by the Investigator.

#### **4.4 PONENTE Long Term Follow Up Substudy: Study Plan and Timing of Procedures**

At the end of the PONENTE EOT visit, patients will be invited to participate in a long term follow up visit 12- to 18-months after completion of the main PONENTE study. This substudy is intended to further assess changes in asthma maintenance therapy in a real-world setting, i.e., according to the treatment prescribed by their healthcare provider. Additionally, there will be assessment of recovery from AI as well as assessment of glucocorticoid toxicity by means of GTI.

Between the EOT visit of the main PONENTE study and the long term follow up visit, patients will be treated according to standard practice; for example, any changes to maintenance asthma regimens are allowed, including further reductions of OCS as recommended in the [GINA 2020](#) report. There will be one on-site visit 12-18 months after the EOT visit of the main PONENTE study. Patients who enrol in the long term follow up visit substudy will still complete the follow-up visit at the end of the main PONENTE study. See Appendix [K](#) for further details.

#### **4.5 Study Conduct Mitigation During Study Disruptions Due to Cases of Civil Crisis, Natural Disaster, or Public Health Crisis**

The guidance given below supersedes instructions provided elsewhere in this CSP and should be implemented only during cases of civil crisis, natural disaster, or public health crisis (eg, during quarantines and resulting site closures, regional travel restrictions, and considerations if site personnel or study patients become infected with severe acute respiratory syndrome coronavirus 2 (SARS-CoV-2) or similar pandemic infection) which would prevent the conduct of study-related activities at study sites, thereby compromising the study site staff or the patient's ability to conduct the study. The investigator or designee should contact the study Sponsor to discuss whether the mitigation plans below should be implemented.

To ensure continuity of the clinical study during a civil crisis, natural disaster, or public health crisis, changes may be implemented to ensure the safety of study patients, maintain compliance with Good Clinical Practice, and minimize risks to study integrity.

Where allowable by local health authorities, ethics committees, healthcare provider guidelines (eg, hospital policies) or local government, these changes may include the following options:

- Obtaining consent for the mitigation procedures (note, in the case of verbal consent, the Informed Consent Form (ICF) should be signed at the patient's next contact with the study site).
- Home or Remote visit: Performed by a site qualified Health Care Professional (HCP) or HCP provided by a third-party vendor (TPV).
- Telemedicine visit: Remote contact with the patients using telecommunications technology including phone calls, virtual or video visits, and mobile health devices.
- At-home Investigational Product (IP) administration: Performed by a site qualified HCP, HCP provided by a TPV, if possible. Additional information related to the visit can be obtained via telemedicine.

For further details on study conduct during civil crisis, natural disaster, or public health crisis, refer to Appendix [L](#).

## **5. STUDY ASSESSMENTS**

The Rave Web-Based Data Capture (WBDC) system will be used for data collection and query handling. The Investigator will ensure that data are recorded on the eCRFs as specified in the Clinical Study Protocol and in accordance with the instructions provided.

The Investigator ensures the accuracy, completeness, and timeliness of the data recorded and of the provision of answers to data queries according to the Clinical Study Agreement. The Investigator will sign the completed eCRFs. A copy of the completed eCRFs will be archived at the study site.

Please refer to Appendix [K](#) for details on study assessments conducted during the PONENTE Long Term Follow Up substudy.

### **5.1 Efficacy assessments**

#### **5.1.1 Assessment of OCS dose**

All patients who meet eligibility criteria and enter the study will receive open-label benralizumab and reduce their OCS dose until the patient reaches an OCS dose of 0 mg/day (or lowest OCS dose possible in case no further OCS down-titration is allowed because of the presence of AI as measured by cortisol levels or in case of inadequate asthma control) as per the details provided in Section [4.2.2](#) and the schedule provided in [Table 2](#) and Section [5.1.2](#)

No further reductions will be made to OCS dose after completion of the reduction phase, and the patient will enter an approximately 24- to 32-week maintenance phase. In case of exacerbations, patients will be managed as per details provided in Section [5.2.3](#). Additionally, in case the patient experiences asthma deterioration or an exacerbation, increase in the maintenance OCS dose is permitted per investigator discretion.

All OCS dose changes will be documented in the source documentation and recorded in the appropriate eCRF form. Moreover, in case of OCS reduction being temporarily interrupted (in case of an exacerbation or asthma deterioration) or permanently interrupted (exacerbation, asthma deterioration, AI based on cortisol tests, or occurrence of an adrenal crisis), the reason should be documented in the appropriate eCRF, and reduction will be done slowly as per [Table 3](#).

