#### **1.4.4 Maintenance phase:**

This phase will start from the time the patient reaches a complete withdrawal of OCS (or lowest possible OCS dose) without worsening of asthma control and as determined by the Investigator (based on the cortisol/ACTH stimulation results). The maintenance phase could be initiated earlier if OCS dose reduction failed due to clinical deterioration or because the patient did not recover from AI.

The length of the maintenance phase will last approximately 24 to 32 weeks. The duration of the maintenance treatment phase will depend on when the patient enters the maintenance phase relative to the dosing cycle of benralizumab. During this phase, patients will continue benralizumab Q8W for 3 doses, and then the End of Treatment (EOT) visit will be scheduled 8 weeks ( $\pm$  7 days) after the last dose of benralizumab.

Patients who have Complete AI or Partial AI at the end of the OCS Reduction phase, will undergo a final morning cortisol test (and if required, ACTH stimulation test for indeterminate result) approximately 1- 2 weeks prior to end of the OCS Maintenance phase.

If an asthma exacerbation occurs during the maintenance phase, the length of the maintenance phase will not be extended.

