b If morning cortisol test results again indicate complete AI at 3 months, the OCS dose will not be modified as this is the final attempt. If morning cortisol test results indicate risk AI, then reductions will be 1 mg Q4W and, if normal, then reductions will be 2.5 mg Q4W.

**Table 3** “Rescue” OCS down-titration after recovery from an asthma exacerbation or deterioration

Initial OCS dose/day	“Rescue” OCS down-titration after recovery from an asthma exacerbation or deterioration to reach an OCS dose of:		
	10 mg	5 mg	0 mg
>20 mg	Reduction of 5 mg Q4W until reaching a dose of 10 mg/day	Reduction of 2.5 mg Q4W until reaching a dose of 5 mg/day	No AI: Reduction of 2.5 mg Q4W Risk AI: 1 mg/day Q4W and repeat test 2 months later a Complete AI: No OCS dose reduction and repeat test 3 months later b
>10 mg to ≤20 mg	Reduction of 5 mg Q4W until reaching a dose of 10 mg/day	Reduction of 2.5 mg Q4W until reaching a dose of 5 mg/day	No AI: Reduction of 2.5 mg Q4W Risk AI: 1 mg/day Q4W and repeat test 2 months later a Complete AI: No OCS dose reduction and repeat test 3 months later b
>5 mg to ≤10 mg		Reduction of 2.5 mg Q4W until reaching a dose of 5 mg/day	No AI: Reduction of 2.5 mg Q4W Risk AI: 1 mg/day Q4W and repeat test 2 months later a Complete AI: No OCS dose reduction and repeat test 3 months later b
5 mg			No AI: Reduction of 2.5 mg Q4W Risk AI: 1 mg/day Q4W and repeat test 2 months later a Complete AI: No OCS dose reduction and repeat test 3 months later b

a After repetition of the test 2 months later, the decision to further reduce OCS dose will be based on the morning cortisol test results. If test results are normal the OCS dose may be reduced directly to 0 mg/day (if patient was receiving ≤3 mg); the patient will continue receiving 1 mg Q4W if still at risk.

b If morning cortisol test results again indicate complete AI at 3 months, the OCS dose will not be modified as this is the last attempt. If morning cortisol test results indicate risk AI, then reductions will be 1 mg Q4W and, if normal, then reductions will be 2.5mg Q4W.

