### **5.1.2.1 Asthma worsening or asthma exacerbation preventing OCS down-titration**

The OCS dose titration will be interrupted in case of one of the following circumstances related to the asthma condition:

- Asthma deterioration will be assessed by the investigators when there is an increase in ACQ-6 scores of  $\geq 0.5$  from the value at Visit 2. If the ACQ-6 score at Visit 2 is missing, the 1st score recorded post-Visit 2 and pre-OCS reduction may be used as baseline value for the 0.5-point increase (note, however, that it will not be used to impute the baseline for ACQ-6 analysis). The Investigator will decide whether the worsening of asthma should lead to an interruption in tapering of OCS dose until asthma control improves.
- In case of an asthma exacerbation that requires treatment with systemic corticosteroids for at least 3 consecutive days, hospitalization, or emergency room admission, the OCS dose titration will be interrupted, and appropriate treatment will be administered as described in Section [5.2.3](#).

After recovery from the first asthma deterioration or exacerbation, patients will be offered to continue OCS tapering down at a slower speed (ie, Q4W); however, in the case of a second event of asthma deterioration or exacerbation, the OCS reduction will be stopped.

The lower OCS dose (0 mg or above, if required to control asthma disease) that is not changed during a period of 4 weeks and that ensures a patient does not suffer from an asthma exacerbation or that avoids the occurrence of an asthma deterioration/worsening requiring an increase in OCS dose, based on investigator criteria, will be considered the final OCS dose of the OCS reduction phase, and, thereafter, the patient will initiate the OCS maintenance phase on that OCS dose.

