### 5.2.1.1 Morning cortisol test (done at “OCS ≤ 5mg/day [morning cortisol]” visit)

For the morning cortisol test, hold OCS dose and other concomitant medications that could interfere with cortisol results per Section 5.2.1. Serum samples for cortisol will be collected between 8 and 9 am and will be sent to a central laboratory for evaluation. Once the results are available, the site will inform the patient of the results via telephone. Depending on the result, the actions that will be implemented are as follows:

- If cortisol levels are within normal range and the patient does not exhibit any signs and/or symptoms of AI, the patient will continue OCS down-titration by 2.5 mg Q4W

- If cortisol levels are within normal range but the patient exhibits signs and/or symptoms of AI, then OCS down-titration should continue at a slower pace (1 mg Q4W).
- If cortisol levels are below the normal range and above the complete AI range (indeterminate result), then the patient will be instructed to maintain the current OCS dose and come back to the site within 1 week for an ACTH stimulation test (Section 5.2.1.2)
- If complete AI is confirmed, sites will inform patients that the OCS dose will remain the same without further reduction until there is evidence of recovery from the complete AI without worsening of asthma control. The morning cortisol test will be repeated 3 months later, and patients will be educated for symptom awareness of adrenal suppression and use of steroid emergency cards. During this repeat test 3 months later, the patient would also repeat all clinical assessments that were done with the initial morning cortisol test (see Table 1). After the repeat morning cortisol test, the site will inform the patient based on the results as follows:
  - If morning cortisol results at 3 months indicate normal cortisol values, then reductions will be 2.5 mg Q4W, and the patient would subsequently move to maintenance phase at OCS 0mg (or lowest possible dose)
  - If morning cortisol tests at 3 months are indeterminate, then reductions will be delayed further, and the patient would return approximately 1-week later for an ACTH stimulation test:
    - If normal result after ACTH stimulation: Reduce by 2.5mg Q4W then move to maintenance phase at 0mg (or lowest possible dose)
    - If the result is Partial AI after ACTH stimulation: Reduce by 1mg Q4W then move to maintenance phase at 0mg (or lowest possible dose)

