    - If complete AI result after ACTH stimulation: OCS dose will not be reduced further, move to maintenance phase at current OCS dose
  - If morning cortisol tests again indicate complete AI at 3 months, the OCS dose will not be modified as this is the final attempt. The patient would move to maintenance phase at OCS 5mg (or lowest possible dose).

Patients who have Partial AI will undergo an additional morning cortisol test (and if required, ACTH stimulation test for indeterminate result) approximately 1-2 weeks prior to the end of the OCS Reduction phase. Patients who have Complete AI or Partial AI at the end of the OCS Reduction Phase, will undergo a final morning cortisol test (and if required, ACTH stimulation test for indeterminate result) approximately 1-2 weeks prior to the end of the Maintenance phase (prior to EOT). In the absence of evidence of HPA axis recovery, corticosteroid supplementation is recommended during situations of stress (ie, fractures, surgery, trauma, labor, invasive dental procedures, severe systemic infections, major burns, and fever  $>38.5^{\circ}\text{C}$ ). Additionally, patients with Partial AI or Complete AI at the end of the Maintenance phase should be referred to an endocrinologist or other appropriate specialist, per Investigator discretion.

Details related to values for normal, partial AI and complete AI are provided in the laboratory manual.

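### Protocol Section 5.1.1 attaches the Table 3 re-taper to permanent as well as temporary interruption of OCS reduction; the conflict matters only for adrenal crisis and is minor

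*Protocol*

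**What the plan says.** Protocol Section 5.1.1 ends with one conditional sentence. Its first limb is temporary interruption, for an exacerbation or asthma deterioration. Its second limb is reduction that is "permanently interrupted (exacerbation, asthma deterioration, AI based on cortisol tests, or occurrence of an adrenal crisis". Two consequences follow for both limbs: record the reason in the eCRF, "and reduction will be done slowly as per" Table 3.

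The title of Table 3 (Section 5.1.2) restricts it to "OCS down-titration after recovery from an asthma exacerbation or deterioration".

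Other sections give stop rules for particular reasons:

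- Section 4.2.2, after a second asthma event: "The OCS dose reduction phase will then be terminated, and the patient will enter the maintenance phase". Section 5.1.2.1 agrees: "in the case of a second event of asthma deterioration or exacerbation, the OCS reduction will be stopped". Section 5.2.3 says the same for a second exacerbation.
- Section 5.2.1.1, on repeat testing: "If morning cortisol tests again indicate complete AI at 3 months, the OCS dose will not be modified as this is the final attempt". Section 5.2.1.2 has parallel text.

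Section 1.4.4 adds that "The maintenance phase could be initiated earlier if OCS dose reduction failed due to clinical deterioration", and gives failure to recover from AI as a further ground. The synopsis agrees.

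**The concern.** A reduction that has been stopped for good cannot also go on slowly. As drafted, the sentence gives both instructions for all four permanent reasons.

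For an asthma event or a cortisol result, a site can go to the more specific section. Adrenal crisis has no such section. Section 1.3 describes crisis as life-threatening, and Appendix J tells sites to think of it whenever a patient becomes acutely ill during steroid withdrawal. An instruction about what happens to the steroid dose after that event should not point two ways. Read literally, it would send a patient who has had a crisis back into a scheduled dose reduction.

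**Working it through.** No figure in the plan is at issue, so the check is of text against text.

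**Step 1. Which permanent reasons are settled elsewhere?**

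| Permanent reason in 5.1.1 | More specific rule | Result |
|---|---|---|
| Exacerbation | 4.2.2, 5.1.2.1, 5.2.3: a second event ends reduction | Overrides the Table 3 clause |
| Asthma deterioration | 4.2.2, 5.1.2.1: same | Overrides it |
| AI on cortisol tests | 5.2.1.1, 5.2.1.2: complete AI on repeat testing means no dose change and a move to maintenance | Overrides it |
| Adrenal crisis | None that names it | 5.1.1 stands alone |

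**Step 2. Where else is adrenal crisis named?** Section 1.1 and Section 1.3 name it as background risk, Section 6.3.6 for adverse event reporting, and Appendix J for recognition and acute treatment. None says whether the taper stops, resumes or changes speed. Crisis is not among the study-drug discontinuation criteria in Section 3.6. The SAP's titration table and final-dose definition (SAP Section 3.1) do not mention it.

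**Step 3. Do the general AI rules fill the gap?** For a patient with normal cortisol but signs or symptoms of AI, Section 5.2.1.1 says "then OCS down-titration should continue at a slower pace (1 mg Q4W"). Sections 5.1.2 and 5.2.1.2 also slow the taper for symptoms. These rules do not name crisis, and they continue the reduction, which conflicts with 5.1.1 listing crisis as a permanent stop.

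**Step 4. What would Table 3 do if applied literally after a crisis?**

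- *Above 5 mg/day.* The columns down to 10 mg and down to 5 mg carry no AI condition. As an illustration, take a patient at 15 mg/day in the band above 10 and up to 20 mg. The first column gives (15 − 10)/5 = 1 reduction and the second gives (10 − 5)/2.5 = 2. That is 3 reductions at four-week intervals with no adrenal check written into the table. Scheduled cortisol testing begins only after four weeks at 5 mg/day.
- *At 5 mg/day or below.* The 0 mg column makes no reduction if complete AI is found, and footnote b makes a repeat finding final. A patient in crisis with that test result is therefore held. Without it, the column directs 2.5 mg or 1 mg every four weeks.

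The literal reading is therefore unsafe in two situations: a crisis above 5 mg/day, and a crisis at or below 5 mg/day without a complete-AI result.

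**The case against.** The strongest reply is that Section 5.1.1 does contain a stop rule for crisis, because it lists crisis among the reasons for permanent interruption. What follows is a misplaced trailing clause, and Table 3's own title shows that it was not written for crisis. This stands. A reader might infer that the protocol has no stop rule for adrenal crisis, or that it requires re-tapering after one. The documents support neither: the listing is itself a stop, and Table 3 has no crisis row.

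Other text also limits the risk:

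- Table 3's 0 mg cells hold the dose for complete AI.
- Section 5.1.1 itself rules out reductions once the reduction phase is complete.
- The synopsis and Section 1.4.4 allow early maintenance when a patient does not recover from AI, and Appendix J equates crisis with acute AI.
- The synopsis and Section 4.2.2 leave each further reduction to the investigator, though mainly in terms of asthma control.
- Figure 1, footnote 1, accepts that other safety matters may alter the schedule, and Appendix J asks for early endocrinology advice.

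Section 5.1.1 is also mainly about documenting the dose; the taper itself is set out in Sections 4.2.2 and 5.1.2. All this makes the practical risk small. It does not repair the sentence. The mitigating text does not say what happens to the taper after a crisis, and the sentence that does name crisis points both ways.

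**Conclusion.** The sentence is wrong as written, and the defect is minor. It contradicts itself for all four permanent reasons. Specific sections resolve three of them. For adrenal crisis, the only text linking the event to the taper lists it as a permanent stop and then adds a clause that does not fit. The intended meaning, stop, is fairly clear. The residual exposure is a crisis above 5 mg/day or one without a complete-AI result.

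A reader might go on to infer an effect on the second primary endpoint, since a dose of 5 mg or less counts there only when AI is the reason for stopping, and the documents do not say whether a stop for crisis counts as AI. The documents do not support a claim of that kind: they give no expected frequency of crisis, so no size can be put on it. No effect on any endpoint, analysis set or estimate is claimed here. The verdict assumes only that sites may read the sentence as it is printed.

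**What to change.** Split the last sentence of Section 5.1.1 in two.

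1. *Temporary interruption after a first exacerbation or deterioration:* record the reason in the eCRF and, once the patient has recovered, resume reduction per Table 3.
2. *Permanent interruption, including adrenal crisis:* record the reason in the eCRF, make no further reduction, and enter the maintenance phase at a dose set by the investigator with endocrinology advice.

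For crisis, entry to maintenance and the way the held dose is set are clarifications, since no existing text states them for that event. A cross-reference from Section 5.2.1 or Appendix J is optional.

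The cost is one sentence divided and one clause added. No procedure or data item is new, because the reason for interruption is already collected.
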